Initial evaluation of each mother's carotenoid status will be obtained prior to starting any study supplements. Subsequent evaluations while participants are taking the study supplements will be performed in conjunction with routine prenatal visits to their Obstetrician, at approximately 22-26 weeks gestational age and again at 37-39 weeks gestational age. All mothers will undergo a final assessment within two weeks of giving birth.

Infants' evaluations will be performed in the first two weeks of life, either during the original hospital stay or at a follow up outpatient clinic visit.

Visit:	Screening/ Baseline	Maternal Supplementation		
	T1	T2	T3	Birth
Timeframe:	Before 14 Wks GA	22-26 Wks GA	37-39 Wks GA	0 to 2 Wks
Informed Consent	X			
Randomization	X			
Maternal visual acuity and contrast sensitivity	X	X	X	X
Maternal nutritional surveys	X	X	X	X
Dilated eye examination	X			
Maternal serum carotenoids	X	X	X	X
Maternal macular pigment imaging	X	X	X	X
Maternal skin carotenoids	X	X	X	X
Dispense prenatal supplement and do pill counts	X	X	X	X
Infant cord blood carotenoids				X
Infant macular pigment imaging				X
Infant foveal imaging (sdOCT)				X
Infant skin carotenoids				X

Unscheduled Visits

Mothers may be seen for Unscheduled Visits if deemed necessary for repeat measurements or follow-up of Adverse Events. If a mother delivers her baby prematurely, she and her infant will remain in the study and will be asked to complete the final study visit.

Description of Study Assessments:

Visual Function - Manifest refraction, and measurement of best-corrected visual acuity and contrast sensitivity of the mothers will be obtained by certified ophthalmic technicians using standardized protocols. The study staff performing visual acuity will be masked to the treatment assignment. Best-corrected visual acuity testing will be assessed on ETDRS back-lit charts starting at a distance of 4 m, and should precede any examination requiring administration of eye drops to dilate the eye or any examination requiring contact with the eye. Contrast sensitivity will be measured by the Pelli-Robson threshold contrast sensitivity chart at 1 m.

Maternal Eye Exam - The complete ophthalmic exam will consist of the following:

- External examination of the eye and adnexa.
- Routine screening for eyelids/pupil responsiveness (including ptosis, abnormal pupil shape, unequal pupils, abnormal reaction to light and afferent pupillary defect).

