Statistical power and sample size (N) for one of the primary outcome measures, maternal skin carotenoids at birth, was determined using data from the previous study by Henriksen et al. (2013) in which the average maternal skin carotenoids \pm SD at birth was 34000 ± 8300 . This value is 20% lower than the University of Utah Moran Eye Center clinic average value of $\sim 42,500$ Raman counts reported for the ancillary AREDS2 study ([name] et al., 2012). With power of 0.90 and alpha 0.05, a sample size of 20 was calculated for each group in order to detect and prevent a 20% decline during pregnancy. In order to accommodate subsequent ineligibility due to premature birth, low birth weight, or other problems ($\sim 10\%$) and to plan for expected noncompliance and loss to follow up ($\sim 20\%$), we intend to enroll 30 subjects in the Carotenoid Supplementation Group and another 30 in the Control Group.

The other outcome measures (maternal ocular carotenoid depletion during pregnancy, infant carotenoid status at birth, and the exploratory outcome measures of foveal maturity at birth and visual function changes during pregnancy) are not as well characterized, but we estimate that a similar sample size of 20 patients per group will be sufficient to detect differences in these indices.

Statistical Analysis Sets

The Intent-to-Treat set will include all randomized subjects who complete the Baseline Visit carotenoid status evaluations and receive study supplements. Subjects will be analyzed by the supplement arm assigned at the Baseline Visit.

A modified Intent-to-Treat set will include all randomized subjects who receive investigational product and complete carotenoid evaluations for at least one trimester study visit while utilizing study supplements.

Efficacy Analyses

The primary, secondary and exploratory efficacy analyses will be performed using the modified Intent-to-Treat subject set. Paired t-tests will compare the carotenoid status at enrollment and at the final study visit of the mothers receiving carotenoid supplementation to mothers not receiving carotenoid supplementation. We will also compare carotenoid status of infants whose mothers received carotenoid supplementation to infants of mothers without carotenoid supplementation. Significance will be set at 2-tailed $P < 0.05$. The associations between maternal and infant carotenoid status will be assessed with regression analysis.

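### All efficacy analyses use a modified ITT set fixed only after randomisation, and the defined ITT set is given no analysis: an avoidable, probably small, selection risk

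*Combined protocol and SAP*

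**What the plan says.** All references are to the combined protocol and SAP.

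Section 4 (Study Information), item 9, Statistical Analysis Sets, defines two sets. The ITT set is "all randomized subjects who complete the Baseline Visit carotenoid status evaluations and receive study supplements", analysed by assigned arm. The modified ITT (mITT) set requires receipt of product and that the woman "complete carotenoid evaluations for at least one trimester study visit while utilizing study supplements". Under Efficacy Analyses the choice is explicit: "The primary, secondary and exploratory efficacy analyses will be performed using the modified Intent-to-Treat subject set". No main or sensitivity analysis is assigned to the ITT set. The full SAP, including rules for missing data, is to be finalised before database lock.

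The Study Visit Schedule (section 4, item 6) says that each mother's initial "carotenoid status will be obtained prior to starting any study supplements". It continues: "Subsequent evaluations while participants are taking the study supplements will be performed in conjunction with routine prenatal visits", "at approximately 22-26 weeks gestational age and again at 37-39 weeks gestational age". A separate sentence covers birth: "All mothers will undergo a final assessment within two weeks of giving birth". The visit table lists "Dispense prenatal supplement and do pill counts" at all four visits, including Birth.

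The primary outcome (section 1, item 6) is change in carotenoid levels from enrolment to the final visit at birth.

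**The concern.** Baseline is measured before the first supplement, so no randomised woman is in the mITT set at the moment of randomisation. She enters it only by what happens later. The primary comparison, however, needs only a baseline and a birth value. The set can therefore drop women for whom the plan already has everything that comparison uses.

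Missing the mid-pregnancy visits may go with diet or health, and so with carotenoid levels. If it also differed by arm, the difference between arms would shift for reasons other than the supplement. Reporting the ITT set alongside would show whether this had happened, but the plan does not commit to that.

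**Working it through.** **1. Which visits qualify.** The mITT wording asks for an evaluation at a trimester visit during supplement use. The schedule uses parallel wording for the 22-26 week (T2) and 37-39 week (T3) visits and describes the birth assessment in its own sentence. The natural reading is that T2 or T3 qualifies and that *utilizing* names the supplementation period. The planned subgroup analysis by compliance fits this, since it presupposes that poor compliers are analysed. What remains open is whether Birth also counts: the table schedules a pill count there, but its column spans were lost in extraction, so it cannot settle the matter.

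**2. Who is affected.** Consider women randomised, given supplements and measured at baseline:

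| Later evaluations | Birth value | In mITT (T2/T3 reading) | Usable for baseline-to-birth change |
|---|---|---|---|
| T2 or T3 | yes | yes | yes |
| T2 or T3 | no | yes | no |
| neither | yes | **no** | **yes** |
| neither | no | no | no |

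Only the third row differs between the sets in that comparison. If Birth counts, this row vanishes.

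**3. The plan's own sample size.** Inputs from item 9: birth mean 34,000, SD 8,300, clinic average 42,500, so the difference is 8,500; two-sided alpha 0.05, power 0.90. Then n = 2 × (8,300 × (1.960 + 1.282) / 8,500)² = 20.04 per arm, against the stated 20. Enrolment: 20 / (0.9 × 0.8) = 27.8, or 20 / 0.7 = 28.6, against the stated 30. Both are consistent. The exact t-test figure is 21.

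**4. Illustrative shift with no true effect.** The documents give no exclusion rates, so the following are assumptions. Let k be the excess exclusions in one arm of 30, and let the gap be the mean difference between included and excluded women. Shift = (k/30) × gap.

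- k = 1, gap 0.5 SD: (1/30) × 4,150 = 138 counts, 1.6% of 8,500.
- k = 2, gap 0.5 SD: (2/30) × 4,150 = 277 counts, 3.3%.
- k = 6, gap 1 SD: (6/30) × 8,300 = 1,660 counts, 19.5%.

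The SD of change is not given. With an assumed T1-to-birth correlation of 0.8 it is 8,300 × √(2 × 0.2) = 5,249. At a correlation of 0.5 it stays 8,300. Two-sided false-positive rates from the noncentral t, with noncentrality shift / (SD × √(2/n)):

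| Case | n per arm | SD 8,300 | SD 5,249 |
|---|---|---|---|
| k = 1, 0.5 SD | 21 | 5.0% | 5.1% |
| k = 2, 0.5 SD | 21 | 5.1% | 5.3% |
| k = 2, 0.5 SD | 27 | 5.2% | 5.4% |
| k = 6, 1 SD | 21 | 9.7% | 17.0% |
| k = 6, 1 SD | 24 | 10.4% | 18.9% |

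These treat the whole gap as arising after T1. If half is already present at T1, the shift in change for k = 1-2 is 69-138 counts; if all of it is, the shift is 0. Equal exclusions with equal gaps in both arms also give 0. The k = 6 case puts the plan's whole allowance of about 20% for noncompliance and loss (6 of 30) into one arm. None of these figures is a bound.

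**5. Power cost of the wider set.** Assume 30 measured per arm and 20% of the active arm with no effect. The difference is 0.8 × 8,500 = 6,800, and power is 0.877 (common SD 8,300) or 0.850 (mixture SD 8,641). Suppose mITT removes the same share from both arms:

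- none removed: loss 0;
- half removed (27 per arm, 11.1% non-users left): mITT power 0.907 or 0.893, loss 0.030 or 0.042;
- all removed (24 per arm): mITT power 0.935, loss 0.058 or 0.085.

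**The case against.** The strongest reply is that the affected group is very narrow. A woman must miss both T2 and T3 and still attend Birth. Bias further requires that such women differ in outcome and that their number differs by arm. The control arm receives a placebo softgel, the trial is double-masked, visits are tied to routine prenatal care, and participants are paid per completed visit. All of this stands, and it is why the risk is called probably small.

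A reader might infer that both the qualifying visit and *utilizing* are undefined, or that women who stop supplements are excluded. The documents do not support that. The schedule's parallel wording largely settles both terms, and no adherence threshold is set. Only the status of Birth is loose.

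It can also be said that item 9 is a summary and that a fuller SAP is promised. That SAP could add an ITT analysis, and it is the right place for the change. But the promise concerns methods and missing data; it does not alter the stated choice of set.

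Finally, the plan's ITT set is itself conditional on completing baseline evaluations and receiving supplements. That is true, but randomisation and first dispensing both fall at T1, so it would differ from an all-randomised set with baseline evaluations only for a woman randomised and not given supplements.

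**Conclusion.** The point holds as a minor-to-moderate one: a cheap improvement. The primary set depends on post-randomisation attendance that the primary comparison does not need, and no analysis is committed to the wider set.

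It would be tempting to conclude that the mITT choice biases the trial or invalidates its result. The documents show no such bias: they give no exclusion rates and no link between exclusion and outcome. Under modest assumed imbalance the false-positive rate is about 5.0-5.4%. It reaches about 10-17% at 21 per arm, or up to about 19% at 24 per arm with the smaller assumed SD, only when the imbalance is extreme. Women without a birth value drop out of the stated t-test under either set, so changing the set alone does not address them.

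**What to change.** In the SAP due before database lock:

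1. Define the primary efficacy set as all randomised women with a baseline carotenoid evaluation, analysed as assigned regardless of later supplement use.
2. Compare arms at the final visit, adjusting for the T1 value, which is already collected. A repeated-measures model using T2, T3 and Birth is optional; it would let women without a birth value contribute. The change of set does not depend on it.
3. Keep mITT as a sensitivity analysis, and state whether Birth qualifies and that *utilizing* names the supplementation period, if that is the intent.

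Separately, the sample-size paragraph budgets for women who become ineligible after enrolment through premature birth or low birth weight, while the Unscheduled Visits text keeps preterm mothers and infants in the study. These passages must be reconciled, and the SAP should say how the observed values of those mothers and infants are analysed.

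The cost is wording and modest modelling, with no new visits or data. The downside is dilution by non-users. Against mITT the power loss is nil if mITT would have kept them, as the natural reading implies for those who attend T2 or T3. It rises to about 0.06-0.08 if 20% are non-users and mITT would have removed all of them.

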Study Protocol and Statistical Analysis Plan for NCT03750968

Lutein & Zeaxanthin in Pregnancy – Carotenoid Supplementation during Pregnancy: Ocular and Systemic Effects

The following pages contain the IRB approved study protocol and statistical analysis plan at the most recent renewal approved on 21 December 2022.

Date: Tuesday, May 2, 2023 2:01:03 PM

[Print](#)
[Close](#)
IRB_00116610
Created: 10/1/2018 12:13 PM

IRB_00116610

1. Contacts and Title

PI: [name]

Submitted: 11/21/2018

Title: Lutein & Zeaxanthin in Pregnancy (L-ZIP) - Carotenoid Supplementation During Pregnancy: Ocular and Systemic Effects

1. Study Introduction

1. Responsible Investigator:

[name]

Email	Training	Col Date
[contact]	7/27/2021 MCG	4/3/2023

a. Position of the Investigator:

- Faculty or Non-Academic Equivalent
- Student
- Staff
- Resident/Fellow
- Other

2. Contact Persons for the Responsible Investigator:

Name	Email	Training
[name]	[contact]	1/30/2023 MCG
[name]	[contact]	CG
[name]	[contact]	1/31/2023 MCG
[name]	[contact]	1/4/2023 MCG
[name]	[contact]	6/17/2022 MCG

3. Guests of the Responsible Investigator:

Last Name	First Name	E-Mail
-----------	------------	--------

There are no items to display

4. What type of application is being submitted?

[New Study Application](#) (or Amendment/Continuing Review)

5. Title Of Study:

Lutein & Zeaxanthin in Pregnancy (L-ZIP) - Carotenoid Supplementation During Pregnancy: Ocular and Systemic Effects

6. Study Purposes and Objectives:

The primary objective of this study is to characterize the carotenoid status of mothers during pregnancy, specifically to determine if prenatal supplementation counteracts maternal systemic and ocular carotenoid depletion.

The primary outcome measure will be change in carotenoid levels from enrollment to final study visit (birth of child) as measured in serum, skin and the macula by high-performance liquid chromatography (HPLC), resonance Raman spectroscopy, and macular pigment imaging, respectively.

7. Is this a multi-site study, where more than one site needs IRB approval?

Yes No

8. Background and Introduction:

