Has the participant selection process overprotected potential subjects who are considered vulnerable so that they are denied opportunities to participate in research?

Yes No

4. Number of participants to be included and/or enrolled in this entire study, across all study locations: 60 mothers and 60 infants

At Utah prior to October 2019: 60 mothers and 60 infants

5. Characteristics of Participants/Inclusion Criteria:

Pregnant women, 18 or older of all races and ethnicities who:

- have an uncomplicated obstetric history
- plan to deliver either vaginally or by Caesarian section at the University of Utah for their current pregnancy

6. Participant Exclusion Criteria:

Women will be excluded if they:

- Have regularly taken carotenoid supplements containing more than 0.5 mg of lutein and/or zeaxanthin daily during the past six months.
- Have significant eye disease associated with macular pigment abnormalities such as Stargardt disease, albinism, or macular telangiectasia type II (MacTel).
- Have any conditions associated with high-risk pregnancies such as adolescent pregnancy, multiparity, current or past history of diabetes, pre-eclampsia, previous premature delivery, drug abuse, or other significant medical illness.

7. Is a substantial percentage of the participant population anticipated to be non-English speaking?

Yes No

Title: Lutein & Zeaxanthin in Pregnancy (L-ZIP) - Carotenoid Supplementation During Pregnancy: Ocular and Systemic Effects

Vulnerable Populations

Justification Requirements for the Inclusion of Vulnerable Populations

1. How does the nature of the research require or justify using the proposed subject population?

The main objectives of the study are to describe mothers' carotenoid status during pregnancy, and the relation between maternal nutritional status and its effect on the newborn.

2. Would it be possible to conduct the study with other, less vulnerable subjects?

Yes No

If yes, justify the inclusion of vulnerable subjects:

3. Is this population being included primarily for the convenience of the researcher?

Yes No

If yes, explain:

Title: Lutein & Zeaxanthin in Pregnancy (L-ZIP) - Carotenoid Supplementation During Pregnancy: Ocular and Systemic Effects

4. Study Information

1. Design of Study (select all that apply):

Non-Experimental and/or Descriptive Research Design:

There are no items to display

Experimental and/or Interventional Research Design:

Blinded Trial (Single or Double Blinded)

Randomized Trial

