Subgroup analyses will be performed to assess the influences of maternal dietary carotenoid intake, compliance with study supplement use, co-existing medical conditions, BMI, infant gender, and other factors on our study results, with proper attention to the effects of multiple tests on the ability to draw conclusions.

The complete statistical analysis plan will be finalized prior to database lock, and will provide statistical methods as well as descriptions of how missing, unused and spurious data will be addressed. Summarization of study data will be prepared of subject demographics, baseline characteristics, and investigational product exposure.

Safety Analyses

Serious and unexpected adverse events will be collected from the time of the first study supplement administration until a subject completes the study or discontinues prematurely. Treatment emergent adverse events (TEAEs) are defined as those AEs that develop or worsen after the first dose of study supplement and up to 30 days beyond the last dose of study medication. The current version of MedDRA will be used to classify all AEs.

Treatment- emergent adverse events will be summarized by System Organ Class and Preferred Term, in accordance with the MedDRA coding dictionary. The number of subjects reporting each AE preferred term will be tabulated for all TEAEs and separately for those considered as related to study treatment by the Principal Investigator. The number of subjects reporting SAEs will also be tabulated. Adverse event summaries will be presented for each treatment group separately.

Adverse events will be summarized by MedDRA coding terms, and separate tabulations also will be produced for related adverse events (those considered by the Investigator as definitively drug related), serious adverse events and discontinuations due to adverse events. Findings from ophthalmologic examinations will be tabulated for changes over time on study. Separate summaries will be prepared for systemic (non-ocular) and ocular AEs, with events in the study eye and non-study eye summarized separately.

Title: Lutein & Zeaxanthin in Pregnancy (L-ZIP) - Carotenoid Supplementation During Pregnancy: Ocular and Systemic Effects

Consent Process

1. The following investigators and internal staff will obtain consent (as indicated on the Study Location and Sponsors Page):

[name]	University of Utah
[name]	University of Utah
[name]	University of Utah
[name]	University of Utah

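### The only test named for the mothers is a paired t-test, which gives no p-value for the difference between the two randomised arms

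*Combined protocol and SAP*

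**What the plan says.** Section 1 (Study Introduction), item 6, sets the objective: "to determine if prenatal supplementation counteracts maternal systemic and ocular carotenoid depletion". The primary outcome is "change in carotenoid levels from enrollment to final study visit (birth of child) as measured in serum, skin and the macula". Section 4 (Study Information), item 1, classes the design as a "Randomized Trial", and no section describes matching mothers across arms.

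Section 4, item 9, Efficacy Analyses, names one test for the mothers: "Paired t-tests will compare the carotenoid status at enrollment and at the final study visit of the mothers receiving carotenoid supplementation to mothers" who do not receive supplementation, at a two-tailed 0.05 level. The next sentence plans a comparison of infants by maternal arm and names no test. The only other method named is regression, and it is for the association between mother and infant.

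Under Sample Size Calculation and Power Considerations in the same item, "a sample size of 20 was calculated for each group in order to detect and prevent a 20% decline during pregnancy". After allowance for losses, "we intend to enroll 30 subjects in the Carotenoid Supplementation Group and another 30 in the Control Group". Details are deferred: "The complete statistical analysis plan will be finalized prior to database lock, and will provide statistical methods".

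**The concern.** Whether supplementation counteracts depletion can be answered only by contrasting the arms. The sentence sets out to make that contrast but names a test that cannot make it. A paired t-test needs pairs, and the only pairs in this trial are the two visits of one mother. Applied to those, it asks whether the mean change in one arm differs from zero. Run in both arms, it gives two p-values, and neither estimates or tests the supplement effect.

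Two things follow. An analyst who follows the text literally has no primary test of the primary question, and may be tempted to conclude benefit because control fell significantly and the supplemented arm did not. An analyst who does not follow it literally must choose a between-arm test that this document does not name, and the candidates differ in power.

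**Working it through.** **Inputs.** From Sample Size Calculation and Power Considerations: mean at birth 34,000 with SD 8,300; clinic reference about 42,500; power 0.90; alpha 0.05; 20 per group. The two-sided level is from Efficacy Analyses. The difference is 42,500 − 34,000 = 8,500, which is 20% of 42,500. The documents give no correlation r between a mother's baseline and final values, so r = 0.3, 0.5 and 0.7 are assumptions, as is an equal SD of 8,300 at both visits.

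**Step 1: reproduce the stated 20.** For two independent groups:

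n per arm = 2 × [(1.960 + 1.2816) × 8,300 / 8,500]² = 20.04.

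This matches the plan's 20 (21 if rounded up; 22 by the t-test, from 21.05). Power at exactly 20 per arm is 89.9% by the normal approximation and 88.4% by the t-test.

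**Step 2: what the named test would have needed.** For a within-arm paired test of the same decline:

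n = [(1.960 + 1.2816) × 8,300 × √(2(1 − r)) / 8,500]² = 14.0, 10.0 and 6.0 at r = 0.3, 0.5 and 0.7.

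It gives 20 only at r = 0. One paired variant comes close: a difference of 6,800 (20% of 34,000) with 8,300 used as the SD of change gives 18. That requires taking 20% of the already reduced birth mean and treating the SD at birth as the SD of change. The independent-groups calculation is the natural source of the 20.

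**Step 3: what separate paired tests could suggest when the supplement does nothing.** This illustrates a rule the plan does not state: declare benefit if control declines significantly and the supplemented arm shows no significant change. Both arms have the same true decline, n = 20 per arm (19 df), and the SD of change is 8,300 × √(2(1 − r)) = 9,821, 8,300 and 6,429. The probability is P(control significantly down) × P(supplemented not significant), from the noncentral t. Simulation agreed within 0.3 percentage points.

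| Common decline (% of 42,500) | r = 0.3 | r = 0.5 | r = 0.7 |
|---|---|---|---|
| 0% | 2.4% | 2.4% | 2.4% |
| 5% | 12.7% | 15.5% | 20.5% |
| 10% | 24.8% | 24.3% | 16.0% |
| 15% | 16.8% | 8.8% | 1.2% |
| 20% | 4.2% | 0.86% | 0.014% |

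The zero-decline row is 0.025 × 0.95 = 2.4%. The maximum is about 0.5 × 0.5 = 25%, reached when each within-arm test has 50% power. A two-sample test of change rejects in about 5% of trials throughout, counting both directions.

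**Step 4: power of valid between-arm tests** at 20 per arm and a difference of 8,500:

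| Test | SD used | r = 0.3 | r = 0.5 | r = 0.7 |
|---|---|---|---|---|
| Two-sample t-test of change | 8,300 × √(2(1 − r)) | 76.0% | 88.4% | 98.3% |
| ANCOVA on final value, baseline as covariate | 8,300 × √(1 − r²) | 91.1% | 95.4% | 99.3% |
| Final value only | 8,300 | 88.4% | 88.4% | 88.4% |

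The stated losses leave 30 × 0.70 = 21 to 30 × 0.9 × 0.8 = 21.6 per arm, so naming a between-arm test calls for no material change in enrolment.

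**The case against.** The strongest reply is that the intent is plain. The sentence says supplemented mothers are compared with unsupplemented mothers, and the word paired may refer loosely to the two visits whose change is compared. On that view the comparison is planned and only its label is wrong. The text is also a summary written for an ethics application. It promises fuller methods before database lock, and the trial is described as double-masked, so a test chosen later need not be driven by the data.

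The point on intent stands, and it makes the wrong test name an error to correct. Intent does not, however, choose between a change score and ANCOVA, which differ by 15 points of power at r = 0.3. The later plan is not in these documents, and the cover presents this text as the approved protocol and statistical analysis plan. A promise of more detail does not withdraw a method already written. Masking and a lock deadline reduce the risk of a data-driven choice, but the documents do not say when the analyst is unmasked.

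Three further points stand as qualifications:

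- The false-pattern figures rest on an unstated rule and an assumed r, and are small at the plan's own 20% decline in the table's r = 0.5 and 0.7 columns. They are illustration only.
- The sample size was set on the value at birth, using the SD at birth. It supports two independent groups, but not change as the quantity compared; a two-sample test of change needs 20.04 × 2(1 − r) = 28.1, 20.0 and 12.0 per arm at r = 0.3, 0.5 and 0.7.
- The modified Intent-to-Treat definition does not itself require a baseline value or a final visit, so the later plan must say how women lacking either are handled.

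**Conclusion.** The concern holds. The only test named for the mothers cannot produce an estimate, interval or p-value for the between-arm effect that the objective asks about, and no other section supplies one. That conclusion rests on the text alone. The sample size, which reproduces at 20.04 per arm for two independent groups, confirms that a between-arm comparison was intended.

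The consequence depends on what is done instead. Judging the arms by their separate p-values could mislead in up to 25% of trials with no supplement effect, mainly when the common decline is smaller than the planned 20%. A valid between-arm test has between 76% and 99% power at 20 per arm, depending on the test and on an assumed r of 0.3 to 0.7. The wording should be corrected before database lock.

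**What to change.** Replace the sentence in Efficacy Analyses with wording such as:

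> For each primary measure, the final-visit value will be compared between arms by ANCOVA with the T1 value as covariate, reporting the adjusted difference and its 95% confidence interval. Within-arm paired t-tests are descriptive only. Infant measures will be compared between arms with two-sample tests.

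A two-sample t-test of each mother's change would also be valid and stays closer to the stated primary outcome. ANCOVA is preferred for its power, not required. Whichever is chosen, carry the same wording into the complete analysis plan before database lock and state there the assumed SD of change or baseline correlation.

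The cost is wording only. The visit schedule already calls for serum, skin and macular measurements in every mother at T1, so no new data, visits or participants are needed.
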